### 3 Objectives and Purpose

Our primary overarching aims/objective are

1. To evaluate the feasibility, acceptability, safety and utility of a BUP 32mg SL loading dose induction strategy in the ED, administered as a BUP+Naloxone formulation;
2. To determine optimal processes for an ED protocol and clinical trial.

We hypothesize that enrollment of 35 ED patients with untreated OUD experiencing opioid withdrawal in an open-label, single arm feasibility study of a rapid BUP induction strategy using a loading dose of BUP SL 32mg will provide the necessary information on the feasibility, acceptability, safety and utility of this treatment approach to identify optimal processes for the development of a treatment initiation protocol suitable for the ED setting so that we can properly plan subsequent large scale clinical trials.

The primary endpoint is a binary global measure of successful rapid induction without clinically significant adverse events. This will be determined during the index visit alone, and will not be influenced by loss to follow up in subsequent research visits. Secondarily, we will use a wide-range of validated subjective, objective, and physiologic measures and patient reported outcomes at the index visit (day 0), during the first week (days 1, 2, and 3), and at day 30 to evaluate changes in opioid withdrawal, craving, level of awareness (level of activation/sedation), and other medication effects and to collect preliminary treatment effect and satisfaction data.

#### 3.1 Primary Objective

1. To estimate the proportion and confidence intervals of participants who have “*successful rapid induction*” (as further defined below) amongst enrolled participants who receive a loading dose of BUP SL 32mg during the ED index visit. Successful rapid induction is defined only be the outcome of the participant’s visit, and not by any following research visits.

Hypothesis: All participants who receive a loading dose of BUP SL 32mg will have successful rapid induction. Successful rapid induction is defined as receiving a total of 32 mg of buprenorphine SL at the index research visit without experiencing a clinically significant serious and/or severe adverse event related to the intervention. Loss to follow up in subsequent research visits will not impact this outcome measure.

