Active use of opioids (within 7 days) will be confirmed by a positive toxicology test and/or by the clinical assessment by the study clinician or ED provider (e.g., self-report plus documented history of opioid use and objective findings consistent with opioid withdrawal). We will not rely on toxicology testing alone as synthetic and semi-synthetic opioids are not reliably detected for up to 7 days using currently available CLIA-waived, rapid toxicology tests. The use of urine and/or saliva toxicology tests that are not CLIA-waived will be for non-clinical, research purposes.

Participants will receive the BUP SL 32mg in divided doses, rather than all at once. If after an initial dose of BUP  $\leq$  8mg SL, a participant experiences over-sedation or another adverse event that would preclude further dosing, such as an allergic reaction, the subsequent dose will not be administered and the patient will be withdrawn from the study. The participant will be reassessed for other possible etiologies for these symptoms (for example, infection can cause sedation or mimic withdrawal). Precipitated withdrawal, however, would not necessarily preclude subsequent BUP dosing. In most cases, the treatment for precipitated withdrawal is to administer additional BUP in higher doses. In other words, the latter BUP 24mg dose would be the treatment for precipitated withdrawal in most cases. The determination of whether a participant who is experiencing apparent precipitated withdrawal should receive additional BUP will be determined on a case-by-case basis at the discretion of the study clinician.

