## 5 Study Endpoints

### 5.1.1 Primary Study Endpoints

#### 1. To estimate the proportion having “*successful rapid induction*”

*Successful Rapid Induction*, the primary study endpoint, is defined as completing rapid induction with a loading dose of BUP SL 32mg without experiencing a clinically significant serious and/or severe adverse event (AE) related to the intervention – specifically, the receipt of a dose of BUP SL greater than 8mg during the Index ED visit. We will determine the proportion of participants who have successful rapid induction during the ED index visit amongst all study participants.

- *Clinically significant adverse events* (AEs) include the following: over-sedation (defined as requiring invasive or non-invasive ventilator support, having a Richmond Agitation-Sedation Scale (RASS) of  $\leq -3$ , and/or clinician determination), hemodynamic instability (e.g., persistent hypotension not attributed to other causes), development of severe precipitated withdrawal

Study Number: s19-01700

Version: 7.0

Version Date: 08/01/2022

(clinician determination), or experiencing other unexpected, SAEs, related to receipt of the second dose of BUP SL (for a total of BUP SL 32mg) as defined in *Section 8.1*. This measure will be assessed at the end of the ED index visit.

- Precipitated withdrawal: Clinicians will assess whether an event is considered precipitated withdrawal. This clinical determination will be based on the severity of the withdrawal signs and symptoms, the rapidity of the onset of withdrawal symptoms, and clinical factors (e.g. timing since last use of an opioid agonist(s), type(s) of opioid agonist, duration of action of opioid agonist(s) used, and route of administration). Scores will be based on objective components, eliminating nausea which can be a side effect of BUP administration. Patients who experience precipitated withdrawal will be treated with ancillary medications.

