### **6.9.4 Dosing and Administration**

All participants will receive a total dose of BUP 32mg sublingually in divided doses during the index ED visit. After the participant has received a total of 8mg (as a single dose or in divided doses), BUP SL 24mg will be administered (i.e., 8mg + 24mg, or 4mg + 4mg +24mg). A dose of up to BUP 8mg SL may be administered by the clinical provider prior to enrollment of the patient-participant (i.e., given clinically, not as a research procedure).

After pre-medication assessments are complete and the participant is confirmed to have a COWS of  $\geq 8$ , the participant will be given BUP SL to reach a dose of 8mg. Starting 30 minutes after BUP administration, the participant will be reassessed for withdrawal severity and any adverse events. As long as there are no unexpected significant adverse events, an additional BUP 24mg SL will be administered. Then, participants will be monitored and reassessed every 30 minutes for a period of at least 90 minutes after receiving the last dose of BUP.

Participants will return on days 1, 2, and 3 for research visits. At those visits, participants will be assessed for opioid withdrawal using the COWS scale. On the first day that the participant has objective signs of opioid withdrawal (via COWS), the [name], who is a licensed physician with an X-waiver for BUP prescription, or another study clinician (with the appropriate license and X-waiver) will electronically send a prescription the participant's preferred outpatient pharmacy for a daily dose of BUP 16mg (BUP or BUP/NX 8/2mg: two SL) to start immediately. Participants will be prescribed a quantity sufficient to ensure medication coverage until the date of their appointment for ongoing treatment with a (non-study) OUD treatment provider. Participants who do not exhibit opioid withdrawal at any of the visits on days 1-3, will be given a prescription upon completion of the day 3 visit with instructions to self-administer upon emergence of symptoms of opioid withdrawal or craving.

All participants will receive a referral to be seen by a provider experienced in treating OUD. Thereafter, continued treatment and specific daily dosage of BUP-NX will be a joint decision between the study participant and the healthcare provider.

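### The primary proportion has two denominators, 32 mg recipients in Section 3.1 and all study participants in 5.1.1, and nothing in the plan says which governs

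*Combined protocol and SAP*

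**What the plan says.** The general aim in Section 3 is "To evaluate the feasibility, acceptability, safety and utility of a BUP 32mg SL loading dose induction strategy in the ED". The primary objective in 3.1 estimates the success proportion, with confidence intervals, "amongst enrolled participants who receive a loading dose of BUP SL 32mg during the ED index visit". Its hypothesis carries the same restriction: "Hypothesis: All participants who receive a loading dose of BUP SL 32mg will have successful rapid induction". Section 3.1 then makes receipt of the load part of success: "Successful rapid induction is defined as receiving a total of 32 mg of buprenorphine SL at the index research visit", together with the absence of a clinically significant related adverse event.

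The endpoint definition in 5.1.1 uses another set: "We will determine the proportion of participants who have successful rapid induction during the ED index visit amongst all study participants". It also words the receipt requirement differently: "specifically, the receipt of a dose of BUP SL greater than 8mg during the Index ED visit". Section 10.1 calls the primary outcome a descriptive proportion and names no denominator or analysis set.

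Four other places decide who can fall between the two sets.

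- Section 6.9.4 states the intention: "All participants will receive a total dose of BUP 32mg sublingually in divided doses during the index ED visit".
- Section 2.1.4 provides that after over-sedation or another precluding event at the first dose "the subsequent dose will not be administered and the patient will be withdrawn from the study". Section 7.4.2 says the same for a qualifying event, and 6.7.1 allows the investigator to terminate participation on this ground.
- Section 6.7.2 continues enrollment toward 35 when participants are withdrawn. It does not say whether those withdrawn remain in the analysis.
- Section 6.1, item 6a, lets a patient enroll below COWS 8 but not receive study medication until 8 is reached. Section 6.4 provides for screen failures after enrollment.

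**The concern.** This is the trial's only primary proportion, and it is meant to inform an ED protocol and a larger trial. Failing to get from the first dose to the full load is a feasibility outcome. If the denominator is limited to people who received 32 mg, the receipt half of the success definition is true for everyone counted, and only an adverse event can produce a failure. First-dose stops then leave both the proportion and its interval.

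The study is open-label and single-arm, so with both denominators written into the plan the choice between them could be made after the results are known. The open question in 6.7.2 adds to this. If withdrawn participants are dropped and further patients enrolled, the 5.1.1 proportion moves toward the 3.1 proportion without anyone having chosen that.

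**Working it through.** **Plan's own figure.** There is none to reproduce. Section 10.1 says there is no power calculation and that 35 was set on feasibility.

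**Inputs.** 35 enrolled (4.1, 6.4, 6.6). The number stopped after the first dose, k, is not in the documents and is assumed. Section 3.1 promises confidence intervals but gives no level or method, so two-sided 95% Clopper-Pearson intervals are assumed. No failure after the second dose is assumed.

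**Step 1: who is counted.**

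| Participant | 3.1, read literally | 5.1.1, read literally |
|---|---|---|
| Receives 32 mg, no qualifying event | in, success | in, success |
| Receives 32 mg, qualifying event | in, not successful | in, not successful |
| Stopped after the first dose | out | in, not successful |
| Enrolled below COWS 8, never reaches 8 | out | in, not successful |
| Screen fail after enrollment | out | not stated |

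Under 5.1.1 a first-dose stop fails through non-receipt, since neither 32 mg nor more than 8 mg was given. This holds only if a withdrawn person still counts as a study participant, which 6.7.2 leaves open.

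**Step 2: effect on the result.** The 3.1 proportion is (35 − k)/(35 − k); the 5.1.1 proportion is (35 − k)/35. For x of n, the lower limit is the 0.025 quantile of Beta(x, n − x + 1) and the upper limit is the 0.975 quantile of Beta(x + 1, n − x). When x = n the lower limit is 0.025^(1/n), for example 0.025^(1/34) = 0.897.

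| k (assumed) | 3.1 | 5.1.1 |
|---|---|---|
| 0 | 35/35 = 100% (90.0 to 100) | 35/35 = 100% (90.0 to 100) |
| 1 | 34/34 = 100% (89.7 to 100) | 34/35 = 97.1% (85.1 to 99.9) |
| 2 | 33/33 = 100% (89.4 to 100) | 33/35 = 94.3% (80.8 to 99.3) |
| 3 | 32/32 = 100% (89.1 to 100) | 32/35 = 91.4% (76.9 to 98.2) |
| 5 | 30/30 = 100% (88.4 to 100) | 30/35 = 85.7% (69.7 to 95.2) |

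Each stop lowers the 5.1.1 estimate by 1/35 = 2.9 percentage points and the 3.1 estimate not at all.

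**Step 3: continued enrollment.** Suppose one participant is added per stop. If the stopped participants are dropped, the result is 35/35 (90.0 to 100) for any k. If they are kept, k = 1 gives 35/36 = 97.2% (85.5 to 99.9) and k = 3 gives 35/38 = 92.1% (78.6 to 98.3).

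**Step 4: how likely the results are to differ.** With an assumed stop probability p per participant, the chance of at least one stop among 35 is 1 − (1 − p)^35. For p = 1%, 2%, 5% and 10% this is 29.7%, 50.7%, 83.4% and 97.5%.

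**Step 5: the three results under the proposed definition.** Take 35 enrolled, one of whom never reaches COWS 8 and has had no BUP, and k = 1. Among 32 mg recipients: 33/33 (89.4 to 100). Primary set: 33/34 = 97.1% (84.7 to 99.9). Every enrolled participant: 33/35 = 94.3% (80.8 to 99.3).

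**The case against.** The strongest reply is that 3.1 is only loosely worded. If receiving a loading dose there means being treated under the strategy, the 32 mg criterion in its success definition has content again, and 3.1 agrees with 5.1.1 and with 6.9.4, which has every participant receiving the load. Section 5.1.1 is the dedicated endpoint section and does name its denominator. This reading is possible and the documents do not exclude it. They do not state it either: the hypothesis repeats the restriction, and 2.1.4, 6.7.1 and 7.4.2 foresee participants who do not get the second dose.

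A second reply is that 6.7.1 supports a recipients-only denominator. It treats the first 8 mg as a standard ED dose, attributes reactions to it to that standard dose, and says only the added 24 mg is under evaluation. That is a fair rationale for a narrower question, and the recipients-only result deserves to be reported. But 5.1.1 does not adopt it as the denominator, and the aim in Section 3 is the feasibility of the whole induction strategy. Which set is primary is a choice, and the plan has to make it.

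Third, first-dose stops would not go unseen. Section 5.1.2 (item 4) collects reasons for not taking part in some or all procedures, and 10.1 tabulates and describes adverse events. This stands. It limits the harm but does not settle what the primary proportion is.

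A reader might go further and infer that a stopped participant can never count as a failure, or that the planned estimate is biased upward. The documents do not support this. It holds only on the literal reading of 3.1, and 5.1.1 says otherwise.

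**Conclusion.** The two denominators are both in the text and nothing reconciles them, so the plan should be corrected. This much is certain. How far the result moves is not, because it depends on a number of first-dose stops that the documents do not give. At k = 0 nothing changes. At one to three stops among 35, the point estimates differ by 2.9 to 8.6 percentage points (100 − 97.1 and 100 − 91.4), and the lower limits by 4.6 to 12.2 points (89.7 − 85.1 and 89.1 − 76.9). These figures rest on no later failure, no added enrollees, and exact 95% intervals.

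The consequence is limited. The study is a descriptive pilot with no test or threshold, the sample size is unaffected, and both proportions can be computed from the same data. The numerator difference is smaller still: 32 mg and more than 8 mg give different answers only if the second dose is partly taken.

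**What to change.** State one primary denominator in 3.1, 5.1.1, 6.7.2 and 10.1. It should be the 5.1.1 set with one restriction, disclosed as such: all enrolled participants who receive BUP at the index visit toward the 32 mg load. BUP given clinically before enrollment (6.9.4) counts only if the participant then has COWS ≥ 8 confirmed and enters study dosing. The text should say what marks entry into study dosing for someone who had already received the full 8 mg clinically.

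- **Keep** in the set everyone later stopped or withdrawn for any reason, including an exclusion criterion first shown by a reaction to BUP. Allergy to BUP is itself an exclusion (6.2), and 6.7.1 allows withdrawal for a newly recognised one, so a first-dose allergic reaction could otherwise be recoded as a screen fail and dropped.
- **Class as screen fails** only participants whose ineligibility rests on facts that predate the first BUP dose and do not depend on the response to it.
- **Count** anyone in the set who does not meet the success definition as not successful. Participants enrolled later under 6.7.2 add to the set and do not replace anyone.
- **Sensitivity result:** the literal 5.1.1 proportion over every enrolled participant. Those who never reach COWS 8 and screen fails count as not successful, with reasons listed.
- **Supportive result:** the proportion among 32 mg recipients, which addresses the added 24 mg (6.7.1).
- **Numerator:** reconcile the wording between 3.1 and 5.1.1.

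These changes concern classification in the analysis only; no dosing, withdrawal or stopping rule is altered. The cost is wording in four sections, one sensitivity proportion and a list of reasons, with no new data. The downside is a possibly less favourable proportion and a denominator that may slightly exceed 35.

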## 6.4 Strategies for Recruitment and Retention

As described previously, potential participants will be identified and screened after presenting to the Bellevue Hospital ED in opioid withdrawal. Using methods employed successfully in our previous and ongoing studies, potential participants will be identified by clinician referral or clinical screening. Patients may be referred to the study team by ED clinicians at NYULH-Tisch, NYULH-Brooklyn, NYULH-Winthrop, and NYULH-Cobble Hill.

The research team will be notified of potential participants and determine whether they meet eligibility criteria. Subjects will be approached by trained research staff who will request the patient's verbal consent to inform them about the study and determine whether they are interested using an IRB-approved verbal consent script. Written informed consent will be obtained before any study activities are performed. After they are consented, we will perform additional assessments to confirm eligibility followed by pre-treatment

Study Number: s19-01700

Version: 7.0

Version Date: 08/01/2022

assessments as detailed in Section 6.9.4: *Dosing and Administration*. Individuals who meet any exclusion criteria will not be enrolled or will be withdrawn from the study if already enrolled as post-enrollment screen fails.

Efforts will be made to maintain contact with patient-participants throughout the duration of the study and to minimize missing data. Broadly, retention methods may include outreach to the participant and their identified contacts through email reminders, phone calls, text messaging, and social media.

A total of 35 participants will be enrolled in the study with the goal of having 30 participants complete the study in its entirety.

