#### **6.7 Participant Withdrawal or Termination**

##### **6.7.1 Reasons for Withdrawal or Termination**

Participants are free to withdraw from participation in the study at any time upon request. An investigator may terminate participation in the study if:

- After the first 8 mg dose of BUP is administered, a study participant experiences any clinical AE (e.g., allergic reaction) that would preclude safe administration of the subsequent BUP 24mg dose during the index visit. The initial BUP 8mg is a standard dose used in the ED; it is only the subsequent BUP 24mg (for a total dose of BUP 32mg) that is being evaluated in this study.
- Thus, if a participant develops a reaction to the initial 8mg dose, the reaction would be attributed to the standard dose of BUP and not the larger dose of being tested.
- The participant meets an exclusion criterion (either newly developed or not previously

Study Number: s19-01700

Version: 7.0

Version Date: 08/01/2022

recognized) that precludes further study participation.

- The participant becomes a prisoner.

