### **6.7.2 Handling of Participant Withdrawals or Termination**

If participants are terminated from the study or withdraw themselves for any of the above reasons, the situation will be handled accordingly. If participants choose to withdraw themselves, but have no AEs, they will still be eligible to continue treatment for OUD, which may include BUP, and will be treated with the standard of care and connected to follow-up as clinic availability allows. If participants are terminated or removed due to any AE, they will be monitored and treated either in the ED or on an outpatient basis. If a participant meets exclusion criteria (either newly developed or not previously recognized), they will be formally withdrawn from the study, but may be still be eligible to continue BUP treatment outside of the study. If participants are withdrawn or discontinued early, enrollment will continue to meet a goal of 35 participants.

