## **7.4 Study Schedule**

### **7.4.1 Screening**

### **7.4.2 Enrollment/Baseline**

#### **Index ED Visit (Day 0, 4 – 8 hours)**

- Perform baseline assessments:
  - Obtain demographic information, medical/psychiatric history, medication history, substance use history.
  - Obtain informed consent of potential participant verified by signature on written informed consent for screening form.
  - Perform medical examinations needed to determine eligibility based on inclusion/exclusion criteria.
  - Review history and verify inclusion/exclusion criteria.
  - Collect urine or saliva samples for toxicology testing, collect urine for a pregnancy test (in females of childbearing potential, if not performed clinically).
  - Assess and quantitate opioid and other substance use, withdrawal, craving, motivation for treatment, health status questionnaire, health services utilization).
- Participants receive total 32mg BUP in divided doses. After the participant has received a total of 8mg, participants will be observed for 30 minutes to ensure that there are no adverse reactions to BUP-NX. If the participant has a qualifying adverse event after the first dose (e.g., allergic reaction or other clinically significant AEs as described in Section 5.1.1), the second dose will not be given and the participant will be withdrawn from the study without receiving subsequent doses. Otherwise, the second dose of 24 mg will be administered.
- Participants will be assessed using opioid withdrawal scales (COWS, SOWS, VAS) prior to BUP administration and every 30 minutes afterward for at least 90 minutes after last dose.
- Participants will be discharged with 4 scheduled appointments, 3 research visits (days 1, 2, 3), an appointment for follow up with a BUP provider for ongoing OUD treatment, and a research follow-up phone call on Day 30, which marks the end of the study for the participant.
- In light of the health safety risks associated with the COVID-19 pandemic, interviews may be conducted remotely, rather than in-person, using an approved, secure audio or audio-video connection (e.g., telephone, Cisco Webex) from a setting offering adequate privacy. Participants will be advised that they may disconnect their video feed.

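### Section 3.1 takes the primary proportion only among 32 mg recipients, so completing the load cannot fail; Section 5.1.1 uses all study participants and leaves the status of withdrawn participants unstated

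*Combined protocol and SAP*

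**What the plan says.** The primary endpoint is described in three places, and the rules on stopping and withdrawal in two more.

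- **Section 3** lists feasibility first among the aims and says: "The primary endpoint is a binary global measure of successful rapid induction without clinically significant adverse events".
- **Section 3.1** estimates the proportion with successful rapid induction "amongst enrolled participants who receive a loading dose of BUP SL 32mg during the ED index visit". Its hypothesis carries the same condition. Success there means a total of 32 mg at the index visit with no clinically significant serious and/or severe adverse event related to the intervention.
- **Section 5.1.1** states: "We will determine the proportion of participants who have successful rapid induction during the ED index visit amongst all study participants". Its definition of success adds "specifically, the receipt of a dose of BUP SL greater than 8mg during the Index ED visit", and its adverse-event list ends with events related to the second dose.
- **Section 7.4.2** covers a qualifying event after the first dose: "the second dose will not be given and the participant will be withdrawn from the study without receiving subsequent doses".
- **Section 6.7.1** attributes first-dose reactions to standard treatment, on the ground that "it is only the subsequent BUP 24mg (for a total dose of BUP 32mg) that is being evaluated in this study".
- **Section 6.7.2** adds: "If participants are withdrawn or discontinued early, enrollment will continue to meet a goal of 35 participants".

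Section 10.1 calls the primary analysis a descriptive proportion of participants successfully induced. It defines no analysis set, and says that the sample size rests on feasibility, without a power calculation.

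**The concern.** Under Section 3.1, receipt of 32 mg is both the entry condition for the denominator and half of the definition of success. That half cannot fail. Only a qualifying adverse event among fully dosed participants can lower the figure, so it stays at 100% however many patients start the load and do not finish it, provided the finishers have no such event. Yet whether patients can complete the load in the ED is central to a feasibility study.

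Section 5.1.1 does not clearly repair this. On its plain reading, a participant stopped at 8 mg is a study participant who was not successful. But Section 7.4.2 withdraws that person, Section 6.7.1 says that only the 24 mg dose is under evaluation, and Section 6.7.2 keeps enrolling toward 35 without saying whether the withdrawn person stays in the denominator. If they are dropped, Section 5.1.1 gives the same figure as Section 3.1.

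Non-completion is foreseeable. The protocol provides for stopping after 8 mg and for voluntary withdrawal at any time. Because the study is open label, the denominator could be settled after the results are known, and this proportion with its interval is the primary result that will inform later trials.

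**Working it through.** **Stated figures.** There is no power or precision calculation to reproduce, since Section 10.1 bases the sample size on feasibility. Section 6.4 fixes the number: "A total of 35 participants will be enrolled in the study". Its goal of 30 finishing refers to the whole study through day 30, not to the dose.

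**Assumptions.** All 35 enrolled are eligible, k of them do not receive the full 32 mg, and a of the 35 − k recipients have a qualifying event. The documents give neither k nor a. They promise confidence intervals but state no level or method; exact (Clopper-Pearson) 95% intervals are used here.

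**Formulas.**

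- Section 3.1: (35 − k − a) / (35 − k)
- Section 5.1.1, plain reading: (35 − k − a) / 35
- Section 5.1.1, withdrawn participants dropped: the same as Section 3.1
- For x successes in n, the lower limit is the 2.5% quantile of Beta(x, n − x + 1) and the upper limit is the 97.5% quantile of Beta(x + 1, n − x). When x = n the lower limit is 0.025^(1/n) and the upper limit is 100%. For 31/31 this gives 0.025^(1/31) = 0.888.

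**Total enrolment fixed at 35.**

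| k | a | Section 3.1 | Section 5.1.1, plain reading |
|---|---|---|---|
| 0 | 0 | 35/35 = 100% (90.0 to 100) | 35/35 = 100% (90.0 to 100) |
| 1 | 0 | 34/34 = 100% (89.7 to 100) | 34/35 = 97.1% (85.1 to 99.9) |
| 2 | 0 | 33/33 = 100% (89.4 to 100) | 33/35 = 94.3% (80.8 to 99.3) |
| 4 | 0 | 31/31 = 100% (88.8 to 100) | 31/35 = 88.6% (73.3 to 96.8) |
| 4 | 1 | 30/31 = 96.8% (83.3 to 99.9) | 30/35 = 85.7% (69.7 to 95.2) |

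**Replacement until 35 are fully dosed** (one reading of Section 6.7.2), with a = 0. Section 3.1 gives 35/35 = 100% (90.0 to 100) for every k. The plain reading of Section 5.1.1 gives 35/(35 + k):

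- k = 1: 35/36 = 97.2% (85.5 to 99.9)
- k = 2: 35/37 = 94.6% (81.8 to 99.3)
- k = 4: 35/39 = 89.7% (75.8 to 97.1)

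**Reading the results.** At k = 4 with no events, the gap is 100 − 88.6 = 11.4 points without replacement and 100 − 89.7 = 10.3 points with it. Replacement therefore does not remove the discrepancy. Section 5.1.1 alone supports either 88.6% or 100% from the same 35 patients, depending on how withdrawn participants are treated.

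**The case against.** The strongest reply is that in a single-arm protocol, receiving 32 mg may simply describe the assigned treatment. Sections 6.9.4, 6.9.7 and 10.2.1 all say that participants will receive the 32 mg dose. Read that way, the two denominators coincide and the dose requirement does real work. But in Section 3.1 the phrase qualifies enrolled participants and so marks out a subset of them, and the protocol elsewhere provides for people who stop at 8 mg. The looser reading is possible, but the text does not say it.

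Other points stand in part:

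- **The 8 mg wording.** The only regimens are 8 + 24 or 4 + 4 + 24 mg, so barring a partly taken 24 mg dose, anyone given a dose above 8 mg has reached 32 mg. Reading Section 5.1.1 as a lower dose requirement would change almost no result. The difference between events related to the intervention and events related to the second dose can be reconciled through Section 6.7.1. Both are matters of tidying.
- **No decision rule.** Section 10.1 judges feasibility on the overall findings, and Section 5.1.2 collects reasons for not taking part in some or all procedures. Non-completion is therefore not lost from the study, and a reader given the counts could recompute either proportion. It would still be absent from the primary estimate and its interval.
- **Attribution.** Treating first-dose reactions as effects of standard care is deliberate. That is sound for a safety estimate of the tested dose, but it is no reason to remove those patients from a measure of whether the load can be completed.

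**Conclusion.** The concern holds. As written, Section 3.1 yields a primary proportion that cannot register failure to complete the load. Section 5.1.1 uses a different denominator, and nothing in Sections 6.7.1, 6.7.2, 7.4.2 or 10.1 settles which applies or where withdrawn participants belong.

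The size depends on k, which the documents do not give. With no qualifying events and enrolment fixed at 35, each non-completer separates the two figures by 1/35, or about 2.9 points. At k = 0, or if withdrawn participants are dropped under both sections, the figures agree. The consequence is a possibly misleading feasibility estimate and a choice left open until the data are seen. It is not a wrong test decision, because the analysis is descriptive and sets no threshold. It should be fixed before analysis.

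**What to change.** - **Sections 3.1, 5.1.1 and 10.1:** use one primary denominator, namely all enrolled participants confirmed eligible, including having reached COWS ≥ 8. Count anyone not given the full 32 mg by the end of the index visit as not successful.
- **Section 6.7.2:** state that withdrawn participants who are replaced remain in this denominator. List post-enrolment screen failures, and those who never reach COWS 8, separately outside it. The latter also bear on feasibility, so their number should be reported beside the primary result.
- **Section 5.1.1:** state that completion means 32 mg, and that the reference to more than 8 mg only identifies the dose to which adverse events are attributed.
- **Safety:** report the event-free proportion among 32 mg recipients as a separate estimate, and apply the Section 6.7.1 attribution rule there. A first-dose reaction then counts as non-completion, not as an adverse event of the tested dose.

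The cost is about one sentence in each of the four sections. Enrolment, eligibility and dosing are already recorded, so no new data are needed. The drawback is that the headline figure may fall below 100%, and reactions to the standard 8 mg dose will lower it as non-completions.
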